6.2. Institutional Review Board (IRB)

After the protocol is finalized and approved by FDA, FDA staff with primary responsibility for the FDA's involvement with the project (i.e., the FDA Project Lead) will submit the protocol and associated documentation to FDA's Office of the Chief Scientist to facilitate an Institutional Review Board Authorization Agreement (IAA) with FDA as the relying institution. The FDA Project Lead or investigator will provide the

local IRB (i.e., Advarra) with all required documents, including the study protocol and informed consent form. The study will not be initiated until appropriate IRB approval is obtained from the local IRB. The investigator will provide the FDA Project Lead with copies of the approval documents for the protocol, informed consent form, and all recruiting materials. The sponsor will provide a copy of the local IRB approval letter to the investigator or designee before the study is initiated. The local IRB will also receive copies of any original or amended information sheets or pamphlets given to the study subject in support of the informed consent process and any advertisements or other recruitment material. Such materials will not be employed in the study before approval by the local IRB.

Subjects will be informed that they have the right to contact the local IRB or Office for Human Research Protections if they have any questions, concerns, complaints, or believe they have been harmed by the participation in this research study as a result of investigator negligence. Subjects will be given the address and phone number of the local IRB.

7. Administrative Procedures

7.1. Responsibilities of the Investigator

The following administrative items are meant to guide the investigator in the conduct of the study but may be subject to change based on industry and government standard operating procedures, working practice documents, or guidelines. Changes may be reported to the IRB but will not result in protocol amendments.

7.1.1 Form FDA 1572

The investigator will complete and sign the Form FDA 1572.

7.1.2 Adherence to Protocol

The investigator agrees to conduct the study as outlined in this protocol in accordance with the ICH E6(R2) and all applicable guidelines and regulations.

7.1.3 Reporting Requirements

By participating in this study, the investigator agrees to submit reports of SAEs according to the time line and method outlined in the protocol (Section 5.7.4.1.2). In addition, the investigator agrees to submit reports to the IRB as appropriate. The investigator also agrees to provide the sponsor with an adequate report shortly after completion of the investigator's participation in the study.

7.1.4 Source Documentation

By participating in this study, the investigator agrees to maintain adequate case histories for the subjects treated as part of the research under this protocol. The investigator agrees to maintain accurate eCRFs and source documentation as part of the case histories.

7.1.5 Retention of Records

The investigator agrees to keep the records stipulated in this protocol and those documents that include (but are not limited to) the study-specific documents, identification log of all participating subjects, medical records, source worksheets, all original signed and dated informed consent forms, subject authorization forms regarding the use of personal health information (if separate from the informed consent form), copies of all eCRFs, query responses, and detailed records of drug disposition, to enable evaluations or audits from regulatory authorities, the sponsor, or its designees.

Furthermore, ICH 4.9.5 requires the investigator to retain essential documents specified in ICH E6(R2) (Section 8) until at least 2 years after the last approval of a marketing application for a specified drug indication being investigated or, if an application is not approved, until at least 2 years after the investigation is discontinued and regulatory authorities are notified. In addition, ICH 4.9.5 states that the study records should be retained until an amount of time specified by applicable regulatory requirements or for a time specified in the clinical study site agreement between the investigator and sponsor.

Refer to the clinical study site agreement for the sponsor's requirements on record retention. The investigator should contact and receive written approval from the sponsor before disposing of any such documents.

7.1.6 Financial Disclosure and Obligations

The investigator is required to provide financial disclosure information to allow the sponsor to submit the complete and accurate certification or disclosure statements required under 45 CFR 46. In addition, the investigator must provide to the sponsor a commitment to update this information promptly if any relevant changes occur during the course of the investigation and for 1 year after the completion of the study.

Neither the sponsor nor the study clinic is financially responsible for further testing or treatment of any medical condition that may be detected during the screening process.

7.2. Confidentiality and Disclosure of Data

All subjects will sign a HIPAA-compliant authorization form containing the mandated core elements and requirements before participation in this clinical study. The sponsor and designees affirm and uphold the principle of the subject's right to protection against invasion of privacy. Throughout this study, a subject's source data will only be linked to

the sponsor's electronic data capture system database or documentation via a unique identification number. As permitted by all applicable laws and regulations, limited subject attributes such as gender, age or date of birth, and subject initials may be used to verify the subject and accuracy of the subject's unique identification number.

To comply with ICH Guidelines for GCP and to verify compliance with this protocol, the sponsor requires that the investigator allow review of the subject's original medical records (source data or documents) by the study monitor, representatives from any regulatory authority (e.g., FDA), the sponsor's designated auditors, and the appropriate IRB. These medical records will include, but will not be limited to, clinical laboratory test result reports, ECG reports, admission and discharge summaries for hospital admissions occurring during a subject's study participation, and autopsy reports. Access to a subject's original medical records requires the specific authorization of the subject as part of the informed consent process.

Copies of any subject source documents that are provided to the sponsor must have certain personally identifiable information removed (i.e., subject name, address, and other identifier fields not collected in the subject's eCRF).

Data will be maintained and backed up in the electronic data capture system. All access to the data is protected by username and password, and each staff member and all sponsor staff will have separate access that requires a separate username and password. Access is only given to site staff and requested sponsor staff who have completed the appropriate training.

7.3. Subject Consent

Written informed consent in compliance with 45 CFR 46 will be obtained from each subject before entering the study or performing any unusual or nonroutine procedure that involves risk to the subject. An informed consent template may be provided by the sponsor to the study clinic. If any institution-specific modifications to study-related procedures are proposed or made by the study clinic, the consent should be reviewed by the sponsor or its designee or both before IRB submission. Once reviewed, the consent will be submitted by the investigator to the IRB for review and approval before the start of the study. If the informed consent form is revised during the course of the study, all active participating subjects must sign the revised form.

Before enrollment, each prospective subject will be given a full explanation of the study and be allowed to read the approved informed consent form. The informed consent process will be performed by a clinical research nurse in a private room. The subject will be given unlimited time to ask questions regarding study participation, and each subject will be questioned to ensure their understanding. Once the investigator is assured that the subject understands the implications of participating in the study, the subject will be asked to give consent to participate in the study by signing the informed consent form.

The investigator will provide a copy of the signed informed consent form to the subject. The original form will be maintained in the subject's medical records at the site.

7.4. Data Collection

Full details of procedures for data collection and handling will be documented in the data management plan, which is initiated with the final protocol receipt. The data management plan is a changing document that evolves over the course of the study and is finalized by database lock.

7.5. Publications

No information related to or generated by this study will be released to the public until it has been reviewed by the sponsor. The sponsor shall own intellectual rights for the data. Authorship on publications will be determined by standard journal requirements.

8. Study Management

8.1. Release of Study Drug to the Study Clinic

Before the study drug can be released to the study clinic, the following documents will be collected from the study clinic by the clinical research organization, retained in the trial master file, and a study drug shipment approval form will be completed by the clinical research organization:

- Protocol signature page signed by the investigator
- IRB approval of the protocol and informed consent form and IRB membership list
- Completed Form FDA 1572, curriculum vitae, and medical licenses from each investigator
- Financial disclosure and debarment certification from each investigator
- Executed contract with investigator and study clinic

8.2. Monitoring

The sponsor or its designee will monitor the study to ensure that it is being conducted according to the protocol, GCP standards, and applicable region-specific requirements, and to ensure that study initiation, conduct, and closure are adequate. The investigators and the study clinic staff will be expected to cooperate fully with the study monitors and personnel or agents of the sponsor and be available during monitoring visits to answer questions sufficiently and to provide any missing information. The investigators and their institutions will permit direct access to source data/documents for study-related monitoring activities, audits, IRB reviews, and regulatory inspections.

During any on-site visits, the study monitor will:

- · Check and assess the progress of the study
- Review all informed consent forms
- Review study data collected
- Conduct source document verification
- Identify any issues and address their resolution
- Verify that the facility remains acceptable
- Conduct study drug accountability

These monitoring activities will be done in order to verify that the:

- Data are authentic, accurate, and complete.
- The safety and rights of the subjects are being protected.
- The study is being conducted in accordance with the currently approved protocol (including any amendments), GCP, and all applicable regulatory requirements.

In addition, the sponsor, designated auditors, and government inspectors must be allowed access to eCRFs, source documents, and other study files that may be required to evaluate the conduct of the study.

8.3. Management of Protocol Amendments and Deviations

8.3.1 Modification of the Protocol

Any changes in this research activity, except those necessary to remove an apparent immediate hazard to the subject, must be submitted to the sponsor or designee and reviewed and approved by the local IRB before implementation. Amendments to the protocol must be submitted in writing to the investigator's IRB for approval before subjects are enrolled into an amended protocol.

8.3.2 Protocol Violations and Deviations

Any significant protocol deviations that the investigator or study clinic staff believes are of major importance (e.g., incorrect randomizations, subject enrolled but not eligible) should be reported to the sponsor and the investigator's IRB as soon as possible. Significant protocol deviations may include the following:

- Deviations from the inclusion/exclusion criteria that may affect subject safety
- Deviations (omission or delay) of safety monitoring procedures
- Deviations in the administration of the study drug
- Deviations in obtaining informed consent

All subjects who are enrolled and receive the study drug, regardless of whether they have a major protocol violation, must continue to be followed for safety for all follow-up study visits.

U.S. Food and Drug Administration Protocol No. SCR-007

9. Appendix

Table 9-1: Schedule of Events by Time Point

	A SERBISER VERTE (NAMED PLE	ON SERVICE PROPERTY VIVE	TOTAL PROPERTY.	ļ			I	I						Will be to b	OTTAIN OF		THE STATE OF	The same	THE SECTION	A 12 TO SEC. A.	PERSONAL STREET	AR STATE BALL	W. A. S.	STATE OF		
	Screening	Checkin / Baseline										۱	reat	Treatment	Period	8										End of Study
Study Week			1				\vdash	 	H			\vdash	-		 	-	H	2	က		2	9	_		Ξ	Day
Study Day	-21 to -2	7	P _{re}		-			-	-	-	-	4	2	8	4	S	2	7	10 1/2	4 21	1 28	35	5 42	93	70	2, 9 8, 9
Hour			٥	0.5	-	7	6	4	9	80	12	24	\vdash	\vdash			-	\vdash	_	\vdash	-	\vdash	_	_		
Visit	-	2						\vdash	\vdash	-						\vdash	_	 	3	\$	9	7	∞	6	2	8, 9, 11
Outpatient visit	×									-	\vdash						Ê	×	×	×	×	×	×	×	×	×
in House Residency		×	×	×	×	×	×	×	×	×	×	×	×	×	×	×	×	-	\vdash	-	-	-				
in formed Consent	×										_		\vdash	-		_				_	-	\vdash	\vdash		ļ	
Medical History	×	×											_	\vdash		-		_	\vdash	_	_	\vdash	_		ļ	
Targeted Physical Exam			×		×		×			×	-		 		-	_	\vdash			_		-				
Comprehensive Physical Examination	×	×									-	×					Ĥ	×			×					×
Vital signs	×	×			×							×			-		Ĥ	×			×	_	L	_		×
12-Lead ECG	×	×										×				\vdash	  ^	×	_		×			_		×
Cinical Chemistry and Hematology	×	×						H				×			_	\vdash	 ^	×			×	L				×
Urinalysis	×	×														_	_		_							×
HIV Ab, HbsAg, HepC Ab	×																									
SARS CoV2 Molecular Test		×											\vdash	_	_	-										
Urine Drug and Alcohol Screen	×	×							-	H		\vdash				_	^	×	H	L		L				×
Pregnancy Test (females only)	×	×										_														×
FSH (females only)	×												-									_				
Drug Administration			×							\vdash		\vdash							H	\vdash	_	\vdash				
PK Concentration/PCSK9 Serum sample			×	×	×	×	×	×	×	×	×	×	×	×	×	×	×	×	×	×	×	×	×	×	×	×
Urine Sample Collection (PD)		×	×									×				-	^	×			×					×
Complete Lipid Profile and ApoB	×	×	×									×	×	×	×	×	×	×	×	X	×	×	×	×	×	×
Genomics (buffy coat)			×																	***************************************						
Proteomics & Small RNA Transcriptomics (plasma)		×	×	×	×	×	×	×	×	×	×	×	×	×	×	×	×	×	×	×	×	×	×	×	×	×
Concomitant Medications	×	×	×								_	×	×	×	×	×	×	×	×	×	×	×	×	×	×	×
A demand of the same	,	>	;	Γ				H	H	-	-	-	-	-	-	-	3	2	,	,	-	;	-	-	2	3

¹ Clinically notable results are repeated 2 Serum test

10.Reference List

- 1. Repatha Package Insert dated 08/27/2015. Found at https://www.accessdata.fda.gov/drugsatfda_docs/label/2015/125522s000lbl.pdf
- Praluent Package Insert dated 07/24/2015. Found at https://www.accessdata.fda.gov/drugsatfda_docs/label/2015/125559Orig1s000lbl edt.pdf

V/F	apparent volume of distribution

Change Log

Version	Section	Changes
02	Appendix	Deleted example randomization schedule
03	5	Added that ‘Subjects who did not complete their treatment (referred to as early termination subjects) will not be included in PK and PD parameter summary calculations.’
03	7.3.1, 7.3.2	The descriptive summary for PD parameters is changed from geometric mean to mean. Changes in PD parameter from baseline for placebo and low doses may have negative values and would not allow for calculation of geometric mean. Text describing the primary, secondary, and exploratory PD parameter was updated for clarity.
03	General	Typographical changes included throughout

1. Introduction

This document outlines the proposed statistical methods for data analysis on data collected from Protocol ‘SCR-007: Pharmacodynamic Biomarkers to Support Biosimilar Development: Clinical Study 2 (PCSK9 Inhibitors – Alirocumab and Evolocumab)’.

2. Study Objectives

2.1. Primary Objective

The primary objective of this study is to report clinical trial operating characteristics for future clinical pharmacology pharmacokinetics (PK) and pharmacodynamics (PD) similarity studies using the different biomarker-based approaches.

2.2. Secondary Objectives

The secondary objectives of this study are:

1. To determine the values and variability of PK and PD parameters at four dose levels (i.e., low, intermediate low, intermediate high, and high doses) for alirocumab and evolocumab.
2. Explore PK/PD relationships using appropriate models for alirocumab and evolocumab.

2.3. Exploratory Objective

The exploratory objectives of this study are:

1. To evaluate the utility of circulating proteins and small RNAs as potential PD biomarkers.
2. To inform analytical approaches and experimental designs needed for identifying exploratory proteomic- and small RNA-based PD biomarkers in plasma

3. Study Overview

3.1. Study Design

This is a randomized, double-blind, placebo-controlled, single-dose, parallel arm, pilot study. Healthy subjects will be randomized to one of four dose groups (low, intermediate low, intermediate high, and high) for each drug (evolocumab or alirocumab) or placebo (See Table 1). The study will be conducted at one center in the United States (Spaulding Clinical Research unit in West Bend, Wisconsin).

All subjects will be sampled daily for the first week. Subjects in groups A, B, E, and F will follow the schedule of events through day 42. Subjects in groups C and G will follow the schedule of events through day 56. Subjects in groups D, H, and I will follow the schedule of events through day 84. Each treatment group should include equal representation of male and female subjects.

Table 1: Study Treatment Groups

Subjects (n)	Treatment Group	Drug
8	A	Evolocumab low (21 mg) subcutaneously (SC)
8	B	Evolocumab intermediate low (35 mg) SC
8	C	Evolocumab intermediate high (70 mg) SC
8	D	Evolocumab high (140 mg) SC
8	E	Alirocumab low (15 mg) SC
8	F	Alirocumab intermediate low (25 mg) SC
8	G	Alirocumab intermediate high (50 mg) SC
8	H	Alirocumab high (100 mg) SC
8	I	Placebo SC

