5.1. Study Design

This is a randomized, placebo-controlled, single-dose, parallel arm study. Healthy subjects will be randomized to four dose groups (low, intermediate low, intermediate high, and high) of each drug (evolocumab or alirocumab) or placebo (See Table 5-1).

Subjects will report to the study site for screening assessments from days -21 to -2 and then will return to the site on day -1 for baseline assessments. Prior to and following study drug or placebo administration on day 1, they will undergo assessments as described in the Schedule of Events (Table 9-1). Subjects will stay in house for the first week and will return to the clinic for study procedures as identified in the Schedule of Events (Table 9-1).

Depending on the treatment arm, subjects will return to the clinic up to 9 times for PK and PD blood draws and additional study procedures as outlined in the Schedule of Events (Table 9-1).

All subjects will be sampled daily for the first week. Subjects in groups A, B, E, and F will follow the schedule of events through day 42. Subjects in groups C and G will follow the schedule of event through day 56. Subjects in groups D, H, and I will follow the schedule of events through day 84. Each treatment group should include equal representation of male and female subjects.

Table 5-1: Study Treatment Groups

Subjects (n)	Treatment Group	Drug
8	A	Evolocumab low (21 mg)
8	В	Evolocumab intermediate low (35 mg)
8	С	Evolocumab intermediate high (70 mg)
8	D	Evolocumab high (140 mg)
8	Е	Alirocumab low (15 mg)
8	F	Alirocumab intermediate low (25 mg)
8	G	Alirocumab intermediate high (50 mg)
8	Н	Alirocumab high (100 mg)
8	I	Placebo

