5.6.3 Study Periods

This is a randomized, placebo-controlled, single-dose, parallel arm study. Healthy subjects will be randomized to four dose groups (low, intermediate low, intermediate high, and high) of each drug (evolocumab and alirocumab) or placebo. Subjects assigned to Groups A, B, E, and F will be kept in the study for 42 days. Subjects assigned to Groups C and G will be kept in the study for 56 days, and the remaining subjects (Groups D, H, I) will remain in the study for 84 days.

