5.8.6 Blinding

The pharmacist (and designated staff member responsible for confirmation of study drug dose) will be unblinded to subject treatment assignment; however, the pharmacist will not perform any study procedures other than study drug preparation and dispensing.

Subjects and staff will be blinded to treatment assignment during confinement. The blind will be maintained through a randomization schedule held by the dispensing pharmacist. Subjects and staff will be informed of a subject's end of study day when discharged from confinement. Subjects and staff will not be informed of the specific treatment arm

assignment. The clinical research nurse will administer the subcutaneous study drug in unit dose containers that are not transparent.

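### Does telling subjects and staff the end-of-study day at discharge make the SAP's double-blind label wrong enough to need a change?

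*SAP*

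**What the plan says.** SAP 3.1 labels the study without qualification: "This is a randomized, double-blind, placebo-controlled, single-dose, parallel arm, pilot study". The SAP has no blinding section; Attachment B mentions only the designated unblinded recipients of the randomization schedule, such as the pharmacist.

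The protocol's design statement in 5.1 does not use the term: "This is a randomized, placebo-controlled, single-dose, parallel arm study". Its blinding rules are in 5.8.6 and have three parts:

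- The period covered: "Subjects and staff will be blinded to treatment assignment during confinement".
- The disclosure: both groups then learn a subject's "end of study day when discharged from confinement".
- What stays hidden: "Subjects and staff will not be informed of the specific treatment arm" assignment.

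Confinement is short. Protocol 5.1 says "Subjects will stay in house for the first week". The end day is tied to the arm in Protocol 5.6.3: "Subjects assigned to Groups A, B, E, and F will be kept in the study for 42 days", and "Subjects assigned to Groups C and G will be kept in the study for 56 days". Groups D, H and I (placebo) stay for 84 days. SAP 3.1 gives the same mapping in the paragraph after the label.

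**The concern.** A reader who sees an unqualified double-blind label on a placebo-controlled trial assumes that active and placebo are masked equally in every arm throughout. Here that holds only for the first week. A subject told Day 42 or Day 56 cannot be on placebo, and staff can deduce this from the protocol they work with.

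The possible harm lies in the safety ratings. Adverse events are recorded until the subject leaves the study (Protocol 5.7.4.1.2), and the investigator rates severity (5.7.4.1.3) and causality (5.7.4.1.4). SAP 7.7.1 tabulates treatment-emergent events by severity, relationship and treatment, and does not mention the disclosure. After discharge, events in six of the eight active arms could be rated by someone who has excluded placebo, while every placebo subject is rated with placebo still possible. If that knowledge shifted ratings, relatedness in those six arms would be inflated relative to placebo.

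**Working it through.** **Inputs.** Nine arms of 8 (Protocol Table 5-1, SAP Table 1); end days by arm (Protocol 5.6.3, SAP 3.1); up to 14 replacements (SAP 3.2). Disclosure is taken as Day 7, inferred from the first week in house.

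**The plan's own figures.** 9 × 8 = 72 and 72 + 14 = 86, which match SAP 3.2.

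**What the end day reveals, at planned allocation:**

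| End day | Groups | Planned n | Chance of placebo | Chance of guessing the exact arm |
|---|---|---|---|---|
| Before disclosure | all nine | 72 | 8/72 = 11% | 1/9 = 11% |
| Day 42 | A, B, E, F | 4 × 8 = 32 | 0 | 8/32 = 25% |
| Day 56 | C, G | 2 × 8 = 16 | 0 | 8/16 = 50% |
| Day 84 | D, H, I | 3 × 8 = 24 | 8/24 = 33% | 8/24 = 33% |

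Placebo can be excluded for 32 + 16 = 48 subjects: 48/72 = 67% of all subjects and 48/64 = 75% of those on active drug. For these 48 the chance of active drug moves from 64/72 = 89% to 100%. In the Day 84 band it falls to 16/24 = 67%.

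**What it does not reveal.** Every band contains both drugs, so the end day never identifies the drug. It fixes the dose level only in the Day 56 band (intermediate high).

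**Follow-up after disclosure, in the 48.** Total: 32 × 42 + 16 × 56 = 2,240 subject-days. After Day 7: 32 × 35 + 16 × 49 = 1,904, or 85%. Discharge on Day 6 gives 32 × 36 + 16 × 50 = 1,952 (87%); on Day 8, 32 × 34 + 16 × 48 = 1,856 (83%). These are shares of calendar time. They do not show where adverse events fall after a single dose, and the documents give no figure for that.

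**Which planned outputs could move:**

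- Primary endpoints (SAP 4.1): LDL-C AUEC and maximum decrease, from laboratory assays.
- Secondary endpoints (SAP 4.2): drug exposure, ApoB metrics and model parameters derived from them.
- Exploratory endpoints (SAP 4.3): PCSK9 metrics, further pharmacokinetic parameters and omics profiles.
- Adverse events (SAP 7.7.1): incidence tables and listings, with no test between arms.

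Only the last involves a rater's judgement.

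**What the suggested edits would do.** Qualifying the label in SAP 3.1 and footnoting the relatedness tables would leave every rating, count and estimate as it is. Only releasing the end day later would change the masking. The stated purpose of that release is not given, but a subject leaving the clinic needs to know how long the outpatient commitment runs, so delay would have to be weighed against retention.

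**The case for a change.** The strongest case for acting is that the inference is certain, not speculative, and the remedy costs one sentence and one footnote. SAP 3.1 and 7.7.1 do not point to Protocol 5.8.6, so someone reading only the SAP's safety tables could assume equal masking. The probably-related category in Protocol 5.7.4.1.4 also refers to known reactions to the product, which may be easier to affirm once placebo is excluded.

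The factual part stands: after discharge, masking of active against placebo is incomplete for two thirds of the planned subjects. Less of the rest does.

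- The SAP and protocol do not conflict. The protocol withholds the specific arm, keeps staff and sponsor blinded when subjects are replaced (5.5.2) and has a full procedure for breaking the blind (5.8.6.1). Calling that double-blind is ordinary usage.
- The causality argument is conjecture. Whether a reaction is known depends on the product's safety profile, the category also requires a distinct temporal relationship, and the rater starts from an 89% chance of active drug. The size of any bias cannot be derived from the documents.
- The footnote could mislead. Placebo and groups D and H share an end day, so the disclosure does not separate them. Saying that this comparison is unaffected, however, could be read as assurance of a full mask. Protocol 5.7.4.2 lists LDL-C among the laboratory tests and has the investigator or designee review laboratory results; the documents do not say that lipid results are withheld.

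**Conclusion.** The concern is factually right but calls for no change. The end day allows placebo to be excluded for 48 of 72 planned subjects, assuming 8 per arm, no replacements and disclosure at about Day 7. With replacements, the count would depend on which arms they join. This is a fair trade-off that the protocol states openly, paired with a short design label that does not repeat it.

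The drug and the specific arm remain undisclosed, the pharmacological endpoints do not depend on a rater's judgement, and the safety output is descriptive. Whoever writes the report can describe the blinding from Protocol 5.8.6 and note, when presenting severity and relatedness after discharge, that active and placebo were not equally masked in all arms. A cross-reference from SAP 3.1 to that section would be a harmless courtesy, provided it does not suggest that placebo against D and H is otherwise fully masked. No planned analysis or result would differ.
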